4.2.3 EXPLORATORY ENDPOINTS

Exploratory Endpoints: Examine all AUD and PTSD outcomes over time between the SL-BUP + XR-NTX and PLC groups at Week 12. As suggested by the Government Steering Committee, some AUD and PTSD measures were added to the study to harmonize with the Simpson-Saxon study. Changes in these exploratory outcome measures from baseline to Week 8 will be compared against the SL-BUP+XR-NTX and PLC groups.

5 STUDY ENROLLMENT AND WITHDRAWAL

5.1 PARTICIPANT INCLUSION CRITERIA

To be enrolled in this study, participants must meet the following criteria.

1. Male or female, 18 to 70 years of age, capable of reading and understanding English, and able to provide written informed consent (i.e., no surrogate).
2. Current moderate to severe AUD as determined by MINI International Neuropsychiatric Interview for DSM-5 (MINI-5).
3. At least two recent episodes of heavy drinking (>5 standard drinks/sessions for men and >4 standard drinks/sessions for women) over the past 30 days, and heavy drinking pattern defined as 14 drinks per week for women and 21 drinks per week for men for at least 2 of a 4-week interval within the 90 days prior to baseline (i.e., at least Moderate Risk level on WHO category).
4. PTSD diagnosis defined by MINI-5 at screening.
5. Clinician Administered PTSD Scale for DSM-5 (CAPS-5) total score ≥ 26 **for the past week** at baseline.
6. Females of child-bearing potential must be using medically acceptable birth control (e.g., oral, implantable, injectable, or transdermal contraceptives; intrauterine device; double-barrier method) AND not be pregnant OR have plans for pregnancy or breastfeeding during the study.
7. Must have a CIWA-Ar score of ≤ 8 prior to randomization.
8. Willing and able to refrain from medications thought to influence alcohol consumption (other formulations of naltrexone, disulfiram, acamprosate, topiramate, ondansetron, and baclofen).

9. Willing and able to refrain from psychotropic medications listed in the prohibited medication list (7.5) that includes opioids, stimulants, Alzheimer's medications, most antipsychotics, benzodiazepines/other sedatives and most mood stabilizers.

Notes:

- Participants may continue stable dose of antidepressants, prazosin, and non-benzodiazepine hypnotics and non-benzodiazepine anxiolytics to treat PTSD or insomnia.
- Stable dose is defined as taken for ≥ 2 months prior to randomization and current dose has been stable for ≥ 3 weeks prior to randomization and held constant during 12 weeks of study medication.)

5.2 PARTICIPANT EXCLUSION CRITERIA

To be enrolled in this study, participants must not meet the following criteria.

1. Current diagnosis of DSM-5 bipolar I, schizophrenia, schizoaffective, and/or major depressive disorder with psychotic features (defined by MINI-5 at screening).
2. Increased risk of suicide that necessitates inpatient treatment or warrants therapy excluded by the protocol, and/or current suicidal plan, per investigator clinical judgement, based on interview and defined on the Columbia Suicidality Severity Rating Scale (C-SSRS).
3. Treatment with trauma-focused therapy for PTSD (e.g., Cognitive Processing Therapy, Prolonged Exposure, or EMDR) within two weeks of baseline study visit. Note: Supportive psychotherapy in process for PTSD at time of Screening may be continued.
4. Current diagnosis of severe non-alcohol substance use disorder (except for caffeine and nicotine) during the preceding 1 month, based on participant screening interview.
5. Use of opioids within 2 weeks of baseline or opioid use disorder in the previous 90 days.
6. History of severe traumatic brain injury (TBI) per Ohio State University TBI Identification Method. Note: history of mild or moderate TBI is allowed.
7. Any clinically significant, uncontrolled, or medical/surgical condition that would contraindicate use of SL-BUP + XR-NTX, or limit ability to complete study assessments, including seizure disorders (other than childhood febrile seizures), severe renal insufficiency, significant arrhythmia or heart block, heart failure, or myocardial infarction within the past 2 years, severe thrombocytopenia or hemophilia, severe hepatic failure, complete hearing loss, and/or need for surgery that might interfere with ability to participate.
8. Clinically significant laboratory abnormalities, including a thyroid stimulating hormone (TSH) >1.5 times upper limit of normal, hyperthyroidism, cardiovascular findings QTcF ≥ 500 msec on electrocardiogram (ECG) or blood pressure $>190/110$, and aspartate aminotransferase and/or alanine aminotransferase > 5 times upper limit of normal.
9. History of allergic reaction, bronchospasm or hypersensitivity to a naltrexone or buprenorphine.

10. Unable or unwilling to refrain from medications thought to influence alcohol consumption (see inclusion criteria above.)
11. Unable or unwilling to refrain from psychotropic medications on the prohibited medication list; with the exception of stable doses of psychotropics listed on the allowed psychotropic medications list.
12. Persons who are imprisoned, of minor age, diagnosed with dementia, diagnosed with a terminal illness, or otherwise require a surrogate to provide informed consent.

Note: Allowance for elevated liver function enzymes, with close medical monitoring, upon enrollment into this study protocol due to the expected impact of heavy drinking in this study population causing transiently high liver function enzymes.

5.3 STRATEGIES FOR RECRUITMENT AND RETENTION

Multipronged Recruitment Strategy: The recruitment strategies include direct recruitment from the investigator's clinics, social media and news advertisement, self-referral through word-of-mouth interactions with others, and integrated outreach to mental health and primary care outpatient clinics, substance rehabilitation programs, community, and inpatient units. The investigators may use social media, advertisements, and commercial services to advertise the study and outreach to potential participants. Under a HIPAA waiver, IRB-approved letters of invitation can be mailed to prospective participants with a past diagnosis of AUD or PTSD who otherwise might meet eligibility criteria. Rate of enrollment at each site is monitored monthly to make sure sites remain on track, and if enrollment is less than 80% of target, for two or more consecutive months, an action plan is developed and implemented. Sites provide cumulative de-identified pre-screening data to the DCC on a monthly basis. This data will allow for the DCC/PASA Consortium to check both site performance metrics as well as help identify any trends in eligibility criteria that could be causing difficulties in enrolling participants into the study.

Retention Strategies: Adherence and attendance is vital to the success of both treatment and the study. Patient education on study procedures and treatment approaches in the study is the cornerstone. As a primary way to minimize drop-out from the study, the investigators and/or Clinical Research Coordinators (CRC) provide thorough pre-enrollment education for all prospective participants during the informed consent process and confirm the participant's commitment to and feasibility for follow-up. Screening and baseline visits are separate from day of randomization so that any ambivalence can manifest, and participants can back-out prior to randomization. The investigators and CRCs also provide ongoing support and education during the study to reinforce the participants' commitment and resolve logistical barriers to keeping the appointments. Participant burden is kept to a minimum (i.e., small number of assessments and low frequency).

To maximize participant retention, CRCs are trained to have a substantial focus, especially in the first several meetings with participants, on developing a strong alliance, educating them about the study, understanding the importance of adhering to treatment, what is expected of

them as a study participant, and eliciting commitment. The investigators also provide ongoing reinforcement of the patients' commitment to long-term follow-up and medication adherence. The study medication and visits are provided at no cost. The study medication providers emphasize the need to properly adhere to prescribed treatments or to call to revise the treatments if side effects occur or therapeutic effects are lost.

The participant receives a modest payment for each attended visit to offset the inconvenience of the follow-up appointments and transportation costs. The site IRBs have approved similar payments in the past and have not viewed the amount as coercive. Service members cannot be paid while on active duty but may be reimbursed for travel costs. Participants are paid more on the days of the psychophysiological testing since these visits require more time. Participants exiting early are encouraged to undergo Week 12 assessments and are paid Week 12 amount.

After consenting to participate, a urine drug screen and breathalyzer will be conducted at each visit. If the drug screen is positive for opiates at screening or baseline visit and/or if the participant has a breathalyzer level > 0.02 at any visit, the appointment will be canceled and rescheduled, and the participant will not be paid for the canceled appointment. The CRC may reschedule the appointment for a later date. If the urine drug screen is positive for opiates at follow-up visits, the investigator must assess the safety of continuing the participant on study medication, but the visit does not need to be canceled.

Schedule of Participation Payments																
	Screening, Baseline, Week (#) or Telephone (T) Visit															
	Screen	Base-line	1	2	T	4	T	6	T	8	T	10	T	12	T	14
Outcome Visits	25	75	25	25		75		25		75		25		50		25
Psychophysiology testing		50 2d								50 2d						

The above payment schedule offers maximum for study participation of \$425 for medication outcomes without psychophysiological assessments and \$525 with psychophysiological assessments. (Note: There is flexibility for sites to adjust their participation payment amounts, for instance West Haven has a minimum payment amount of \$25)

Also, sites can pay for transportation or provide a \$25 gas/gift card to offset transportation costs if needed, at the discretion of investigator and TREAC Executive Director.

5.4 PARTICIPANT WITHDRAWAL OR TERMINATION

5.4.1 REASONS FOR WITHDRAWAL OR TERMINATION

Participants may discontinue study treatment or withdraw from participation in the study at any time without cause or reason. Participants may stop study medication but are encouraged to

remain in the study for follow-up assessments. The investigator may discontinue study treatment for a participant or withdraw a participant from the study for one or more of the following reasons:

- The participant's expressed desire to end his/her participation in the study.
 - Note: The participant may choose to stop the study drug but continue in the study for data collection and is thus not withdrawn from the study.
- A clinically significant adverse event (AE), laboratory abnormality, or other medical condition or situation that makes continued participation in the study to be not in the best interest of the participant
- The participant demonstrates an inability to comply with the verbal and written study instructions and/or procedures, (i.e., loses the capacity to provide informed consent)
- The participant exhibits unsafe behaviors (e.g., abusive, aggressive) or becomes suicidal, homicidal, or psychotic, (i.e., at significant risk of harming self or others).
- The participant has an intolerable adverse reaction to a study medication.
- The participant's underlying condition is worsening and needs alternative treatment(s)
- The study is canceled by the PASA Consortium, DoD, or investigators.
- The study is closed by the Data Safety and Monitoring Board (DSMB), Institutional Review Board (IRB), or other oversight committee.
- New information regarding the safety of a study medication emerges that changes the risk benefit profile for a sub-group of participants

5.4.2 HANDLING OF PARTICIPANT WITHDRAWALS OR TERMINATION

If an early exit occurs, the reason(s) for early termination is documented and all Week 12 procedures are conducted. A post-study phone call or visit is scheduled with the research team to ensure that the participant has made or scheduled the appropriate follow-up appointments and to address any clinical problems or AEs that may have occurred.

Participants may stop study medication but are encouraged to remain in the study for follow-up assessments. In this case, the participant may attend assessments for data collection or consent to allow for continued follow-up through chart review. If a participant withdraws from the interventional portion of a study and does not consent to continued follow-up of associated clinical outcome information, then the investigators will not access the participant's medical record or make future contact with the participant. If a study participant withdraws consent for study participation, then the participant is excluded from all future study procedures and treatments. No additional study data is collected from the participant after consent has been withdrawn.

5.5 PREMATURE TERMINATION OR SUSPENSION OF STUDY

This study may be suspended or prematurely terminated if there is reasonable cause. Written notification, documenting the reason for study suspension or termination, will be provided by the suspending or terminating party to the investigator, DoD Grants Officer Representative (GOR) for further distribution to the Government Steering Committee (GSC), PASA

Consortium PI (or designee), DSMB, and regulatory authorities. If the study is prematurely terminated or suspended, the PI will promptly inform the IRB and will provide the reason(s) for the termination or suspension.

Circumstances that may warrant termination or suspension include, but are not limited to:

- ❖ A pattern of AEs indicating that the selected dose of SL-BUP + XR-NTX is inappropriate or unsafe
- ❖ Determination of unexpected, significant, or unacceptable risk to participants
- ❖ New information emerges that suggests the risks are increased beyond an acceptable limit and outweigh benefits
- ❖ Significant and recurring protocol violations that threaten the integrity of the study data
- ❖ Data that are not sufficiently complete and/or evaluable
- ❖ Continuing and ongoing serious noncompliance with human research protections and regulations that warrants study closure
- ❖ Determination of futility. While there are no formal assessments of futility for efficacy, the study may be terminated if operationally futile, (e.g., there is an inability to enroll or retain study participants). The study may resume once concerns about safety, protocol compliance, data quality is addressed and satisfy the PASA Consortium, IRB and/or other regulatory agencies.
- ❖ Generally, any study suspension that could occur will be based upon review of the study and recommendations made by the DSMB. Details of safety oversight and associated study halting rules are provided in Sections 8.6 and 8.5, respectively.
- ❖ A local site that is not performing for one of the reasons above, may be selectively terminated and replaced with a new site.

6 STUDY AGENTS

6.1 STUDY AGENT(S) AND CONTROL DESCRIPTION

6.1.1 ACQUISITION

XR-NTX and XR-PLC are donated by Alkermes, Inc; and will be sent by Alkermes to the local site pharmacies.

SL-BUP is purchased by each local site's pharmacy from a manufacturer of generic formulation.

SL-PLC is donated to the study by TONIX Pharmaceuticals; and will be distributed through Tuscaloosa VA pharmacy to the West Haven VA.

6.1.2 FORMULATION, APPEARANCE, PACKAGING, AND LABELING

XR-NTX (naltrexone for extended-release injectable suspension, VIVITROL) is supplied as a single use kit containing one 380 mg vial of VIVITROL microspheres, one vial of diluent, one 5-mL syringe, one ½-inch 20-gauge preparation needle, and two 1½-inch 20-gauge administration needles with safety device. VIVITROL microspheres consist of a sterile, off-white to light-tan

powder that is available in a dosage strength of 380-mg naltrexone per vial. Naltrexone is incorporated in 75:25 polylactide-co-glycolide (PLG) at a concentration of 337 mg of naltrexone per gram of microspheres. The diluent is a clear, colorless solution. The composition of the diluent includes carboxymethylcellulose sodium salt, polysorbate 20, sodium chloride, and water for injection.

SL-BUP (sublingual buprenorphine tablet; SUBUTEX) is supplied as an uncoated oval white tablet in counts of 30 tablets per bottle in 2mg/sublingual tablet dosage. SL-BUP contains no naloxone.

SL-PLC is supplied in 40 tablets per bottle that contains 1-gram Sorb-it canister desiccant and polyester coil. The pill is yellow, T debossed on one side, plain on the other side, 4mm diameter x 2.5mm thick.

6.1.3 PRODUCT STORAGE AND STABILITY

Investigational products are for investigational use only and are to be used only within the context of this study. The study drug supplied for this study must be maintained under adequate security and stored under conditions specified on the label until dispensed for participant use or destroyed per instructions from PASA Consortium Leadership and according to local regulations. Product is stored in a limited-access location in the local site VA pharmacies.

The entire dose pack of XR-NTX should be stored in the refrigerator (2 - 8°C, 36 - 46°F). Unrefrigerated, XR-NTX can be stored at temperatures not exceeding 25°C (77°F) for no more than 7 days prior to administration. Do not expose the product to temperatures above 25°C (77°F). XR-NTX should not be frozen.

The SL-BUP and SL-PLC should be stored at 25°C (77°F) and excursions are permitted to 15°-30°C (59°-86°F).

6.1.4 PREPARATION

The XR-NTX microspheres must be suspended in the diluent prior to injection. Parenteral products should be visually inspected for particulate matter and discoloration prior to administration whenever solution and container permit. A properly mixed suspension is milky white, does not contain clumps, and moves freely down the wall of the vial.

SL-BUP has no preparation requirements.

6.1.5 DOSING AND ADMINISTRATION

The dose of XR-NTX is 380 mg delivered intramuscularly [gluteal; alternating buttocks for each subsequent injection and documentation of injection site and date in the Computerized Patient Record System (CPRS) source notes] every 4 weeks or once a month by research MD, APN or RN. XR-NTX and XR-PLC must be suspended **only** in the diluent supplied in the dose kit and must be administered with the needle supplied in the dose kit. All components (i.e., the microspheres, diluent, preparation needle, and an administration needle with safety device) are required for administration. A spare administration needle is provided in case of clogging. Do not substitute any other components for the components of the dose kit.

SL-BUP or SL-PLC will be ordered by an investigator/co-investigator with prescribing privileges in the quantity of pills (one per day) needed for the exact number of days until the next scheduled visit (may vary according to patient needs and location, (i.e., can dispense a four-week supply with number of tablets needed until next scheduled visit for the injection). The local pharmacy or research pharmacist dispenses the medication. The medication management provider and/or the research coordinator reviews the medication instructions with the participant. The participant is informed that he/she must bring any unused portion of the study medication to subsequent visits so that the prescriber can issue the correct number of pills to allow for enough supply to last until the next scheduled visit. Also, the participant is informed that if she/he misses a dose, she/he should take the next dose as soon as possible.

If for any reason there is SL-BUP or SL-PLC study medication that will go unused, the participant will place the unused medication in a Take-Away Medication Recovery System tamper-resistant envelope and place in a US postal service mailbox to be sent to a pharmacy destruction service. This can vary by site and may be done at each visit and/or at the end of the study.

6.1.6 ROUTE OF ADMINISTRATION

XR-NTX or XR-PLC should be administered by a health care professional as an intramuscular (IM) gluteal injection, alternating buttocks, using the manufacturer's kits provided.

SL-BUP or SL-PLC is taken sublingually by the participant, (i.e., placed and held under the tongue until it is dissolved); swallowing the tablet reduces the bioavailability of the drug.

6.1.7 DOSE

Pretreatment with oral naltrexone is not required before using XR-NTX. XR-NTX starting dose is 380mg IM every four weeks. The dose is held constant for the duration of the study treatment period.

SL-BUP is started at 2mg daily and the dose is held constant for the duration of the study treatment period.

6.1.8 DOSE ADJUSTMENTS/MODIFICATIONS/DELAYS

If a participant misses a dose, he/she should be instructed to receive the next dose ASAP.

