2.3 POTENTIAL RISKS AND BENEFITS

2.3.1 POTENTIAL RISKS

Naltrexone for extended-release injectable suspension (XR-NTX; Vivitrol) is FDA-indicated for the treatment of alcohol dependence, so participants in this study may have direct benefit from this treatment. XR-NTX is not a controlled substance.

Sublingual buprenorphine (SL-BUP) is FDA-indicated for the treatment of opioid dependence. SL-BUP is a Schedule III narcotic under the Controlled Substances Act. The use of SL-BUP in a non-opioid dependent population has a risk of misuse or abuse. Buprenorphine is a partial agonist at the mu-opioid receptor and chronic administration produces physical dependence of the opioid type, characterized by withdrawal signs and symptoms upon abrupt discontinuation or rapid taper. The withdrawal syndrome is typically milder than seen with full agonists and may be delayed in onset. However, to mitigate the potential for misuse, dependency, and withdrawal, buprenorphine can be combined with XR-NTX, a medication that blocks the mu receptor involved in psychogenic properties of buprenorphine.

XR-NTX can antagonize the effects of opioids via competitive inhibition of opioid receptors, which raises the concern that the combination of SL-BUP and XR-NTX will make SL-BUP less effective. This would be a risk for individuals who are using opiates or SL-BUP on a regular basis prior to starting XR-NTX, (i.e., the addition of XR-NTX may precipitate opioid withdrawal symptoms). For this reason, this study excludes patients who have recent opioid use or opioid use disorders, and opiates are not allowed to be concurrently taken during the study. XR-NTX is contraindicated in patients receiving opioid analgesics and in patients with current physiologic opioid dependence, acute opiate withdrawal, acute hepatitis or liver failure, and previous hypersensitivity reaction to XR-NTX. Patients with these contraindications are not eligible to participate in this study.

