The investigators have designed the study to include two weeks (from Week 12 to Week 14) to monitor the patient for drug discontinuation or withdrawal symptoms. The investigators will treat emergent psychological symptoms with psychosocial support and physical symptoms with the appropriate treatments, such as metoclopramide for nausea, NSAIDs for pain, clonidine for opioid-like withdrawal symptoms, and loperamide for diarrhea. Three to five days after Week 12 discontinuation of medication, the research nurse will call participant to check on emergent adverse symptoms

A caution that is included in the informed consent stating that in a situation when analgesia may be required in a patient who has received full blocking doses of XR-NTX, consideration should be given to regional analgesia, conscious sedation with a benzodiazepine, use of non-opioid analgesics, or general anesthesia. If opioid analgesia is required, the amount of opioid needed may be greater than usual, and the resulting respiratory depression may be deeper and more prolonged. In this case, a rapidly acting opioid analgesic that minimizes the duration of respiratory depression is preferred. XR-NTX can also diminish the benefit from opioid-containing cough, cold, and antidiarrheal preparations, which is listed as a warning in the informed consent. These warning are standard when treating patients with XR-NTX.

Side effects of XR-NTX that led to more discontinuation of treatment compared to placebo include the following: pain, tenderness, induration or pruritus at the site of the injection (3%), nausea (2%), headache (1%), and suicide-related events (0.3%). Other known non-serious side effects that differ from placebo include nausea (29% vs 11%), vomiting (12% vs 6%), diarrhea (13% vs 10%), abdominal pain (11% vs 8%), injection site reactions (65% vs 50%), arthralgia/arthritis (9% vs 5%), muscle cramps (5% vs 1%), rash (6% vs 4%), headache (21% vs

18%) dizziness (13% vs 4%), somnolence/sedation (5% vs 1%), and appetite decrease (11% vs 3%). XR-NTX has the capacity to cause hepatocellular injury when given in excessive doses (the margin of separation between the apparently safe dose of naltrexone and the dose causing hepatic injury appears to be five-fold. XR-NTX does not appear to be a hepatotoxin at the recommended doses used in this study.

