7.3.3 BASELINE AND RANDOMIZATION VISITS

The investigators and CRCs provide ongoing support and education during the study to reinforce the participants' commitment and resolve logistical barriers to keeping the appointments. Participant burden is kept to a minimum (i.e., small number of assessments and low frequency). Adherence and attendance are vital to the success of both treatment and the study. Patient education on study procedures and the treatment approach in the study is the cornerstone to promote adherence. To maximize participant retention, study coordinators are trained to have a substantial focus, especially in the first several meetings with participants, on developing a strong alliance, educating them about the study, understanding the importance of adhering to treatment, what is expected of them as a study participant, and eliciting commitment.

At the baseline visit, the research team evaluates the participant per the study instruments listed in the Schedule of Assessments table in 7.3.1. Participants undergoing the optional two-day psychophysiological assessments, as described above, will complete both days of the psychophysiological testing prior to beginning the study medication.

The research medication provider enters the medication orders (one for XR-NTX and one for SL-BUP) and the local site pharmacy dispenses the study medication according to the randomized assignment to one of two treatments:

- **Treatment A (SL-BUP 2mg + XR-NTX 380mg) or**
- **Treatment B (SL-PLC and XR-PLC).**

SL-BUP is taken daily and XR-NTX is given every 4 weeks. All medications are dispensed by local site pharmacies with clearly labeled instructions.

The participant receives the first dose of XR-NTX injectable in the research clinic and remains in the clinic under the supervision of the research team for approximately 1 hour after the 1st dose is administered.

The medication provider or trained CRC reviews the medication instructions with the participant (how to administer sublingual, keeping up with medication dosing, and need to return any

unused medication to the research medication provider at the next visit). The participant initiates SL-BUP on the following day.

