7.3.4 FOLLOW-UP VISITS

Assessments occur at screening, baseline, and post-randomization Weeks 1, 2, 4, 6, 8, 10, and 12. There is a visit window of +/- 7 days for follow-up visits.

The investigators and CRCs provide ongoing reinforcement of the patients' commitment to long-term follow-up. The study medication providers emphasize the need to properly adhere to prescribed treatments or to call to revise the treatments if side effects occur or therapeutic effects are lost.

Adherence to SL-BUP medication is confirmed by pill count. Concomitant medications are updated at each of these visits.

If participants experience side effects that cannot be managed by adjustments in the timing of the medication (i.e., taking at bedtime, etc.), they may have their medication titration either held or the medication dosing may be decreased (i.e., less frequent).

The CRC makes a telephone (t) contact with the participant between face-to-face visits to remind the participant of the next office visit and to check on adherence to the study medication and if there have been any serious adverse events.

*Psychophysiological assessments are optional to not be a barrier to enrollment or randomization.

The one-day psychophysiological assessment is repeated at Week 2.

The two-day psychophysiological assessment is repeated at Week 8.

At Week 8, the participant remains on the assigned treatment and dose from Week 8 to Week 12.

While every attempt is made to retain the participant in the study on medication for the full 12 weeks, the participant may discontinue medication at any point and remain in the study for assessments through Week 12.

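### Nothing after the first dose makes the buprenorphine tablets conditional on the naltrexone injection that the protocol's safety argument relies on

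*Protocol*

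**What the plan says.** **The safety premise.** Protocol 2.3.1 says of buprenorphine that "chronic administration produces physical dependence of the opioid type" and names XR-NTX as the mitigation. Sections 2.3.1 and 8.7 then state that the protection lasts as long as SL-BUP is taken and that the addiction risk is thereby eliminated. Both sections also identify a risk for people "using opiates or SL-BUP on a regular basis prior to starting XR-NTX, (i.e., the addition of XR-NTX may precipitate opioid withdrawal symptoms".

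**How the first dose is protected.** Section 5.2 excludes "Use of opioids within 2 weeks of baseline or opioid use disorder in the previous 90 days". COWS is done at screening (7.3.1). The first injection is given in clinic, and 7.3.3 adds: "The participant initiates SL-BUP on the following day".

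**What governs later doses.** Section 6.1.7 sets injections every four weeks and a constant daily SL-BUP dose. Section 7.3.1 schedules dispensing at Baseline, Week 4 and Week 8. Section 6.1.8 consists of one sentence: "If a participant misses a dose, he/she should be instructed to receive the next dose ASAP". Section 6.1.5 repeats it for tablets. Section 7.3.4 says every attempt is made to keep participants on medication for 12 weeks. Sections 5.4.1 and 7.3.4 allow medication to be stopped but do not distinguish the two drugs.

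**The concern.** The claim of full-duration protection is true only if nobody takes SL-BUP without a current injection. The plan enforces that order once, at baseline, and then treats the two drugs as independent. No provision says that tablets stop when an injection is refused, withheld or given up. None sets a maximum gap or asks for a check before a late injection.

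What is at stake is participant safety. SL-BUP without cover is the exposure that the protocol says XR-NTX is there to mitigate, in a population in which drinking is expected. Protocol 2.3.1 also warns of respiratory depression and death when buprenorphine is combined with alcohol. A later injection after a long uncovered period resembles the sequence that 2.3.1 links to precipitated withdrawal. Sites could reasonably handle the same situation differently.

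**Working it through.** There is no stated figure to reproduce. The check has two parts.

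**1. Is there a linking rule?** The provisions that could contain one, side by side:

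- 6.1.7: SL-BUP is daily and constant, with no condition on the injection.
- 6.1.8 and 6.1.5: next dose as soon as possible; silent on the other drug.
- 6.1.5: tablets are ordered to last until the next scheduled visit. This limits quantity but does not require that the injection was given.
- 7.3.1: tablets are dispensed at the injection visits. COWS is scheduled at screening, Week 12 and Week 14 only.
- 5.4.1 and 7.3.4: medication may be stopped; components are not separated.

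None of them makes tablets conditional on the injection. Followed literally, a participant who attends Week 4, declines the injection and accepts tablets is within the written dosing rules for SL-BUP.

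**2. How long could SL-BUP outlast the injection interval?** Inputs: injections due on days 0, 28 and 56; treatment ends on day 84; visit window ±7 days (7.3.4); interval 28 days (6.1.7). The windows are therefore Week 4 = days 21 to 35, Week 8 = days 49 to 63, and Week 12 = days 77 to 91.

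Days beyond the interval = (day of next injection or end of tablets) − (day of last injection) − 28.

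| Scenario, tablets continuing | Nominal | Range across windows |
|---|---|---|
| Week 4 injection not given, next at Week 8 | 56 − 0 − 28 = 28 | 49 − 28 = 21 to 63 − 28 = 35 |
| Injections stop after baseline | 84 − 0 − 28 = 56 | 77 − 28 = 49 to 91 − 28 = 63 |

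Section 6.1.5 also allows once a month. At 31 days the results are 25 (18 to 32) and 53 (46 to 60).

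For comparison, with no injection missed, Week 4 at day 21 and Week 8 at day 63 give 63 − 21 − 28 = 14 days beyond the interval, within the windows.

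Only the first scenario includes a later injection, so only it bears on precipitated withdrawal. The second concerns uncovered exposure alone.

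**The case against.** The strongest reply is that most routes to SL-BUP without an injection are already closed.

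- **Missed or cancelled visits.** Protocol 5.3 says that "if the participant has a breathalyzer level > 0.02 at any visit, the appointment will be canceled and rescheduled", which includes injection visits. A reader might infer long uncovered gaps in people who are drinking. The documents largely contain this. Tablets are counted to the next scheduled visit (6.1.5), dispensing falls on the injection visits, and out-of-window visits are reportable deviations (SAP 7.9). A cancelled visit therefore delays the tablets too. This part of the reply stands.
- **Reduced dosing.** Section 7.3.4 says "the medication dosing may be decreased (i.e., less frequent". In context this follows an example about bedtime dosing and describes tablets. Fewer tablets is not SL-BUP without an injection. This also stands.
- **Visibility.** A reader might infer that the overlap could never be seen. SAP 8.3 plans a listing of missed doses with reasons, and Appendix A(e) gives the DSMB all deviations. The overlap could be reconstructed, although no planned summary shows it.
- **Clinical judgement.** A qualified provider sees participants at each visit (7.1.3), investigators may stop treatment (5.4.1), and study medication could naturally be read as both drugs. That is a fair reading, but it is not written as a rule.

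The reply does not reach the attended visit at which the injection is refused, withheld or stopped and tablets are still ordered. The statement in 2.3.1 that withdrawal is highly unlikely at this dose does not reach it either: it concerns stopping SL-BUP, especially with naltrexone present, not adding naltrexone.

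**Conclusion.** The point holds for attended visits without an injection. The protocol's safety premise is asserted for the whole treatment period but enforced only at the first dose. If tablets continue, SL-BUP runs 28 days (21 to 35) past the interval when the Week 4 injection is not given and the next is at Week 8. It runs 56 days (49 to 63) when injections stop after baseline.

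Two stronger readings are not supported:

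- **That the missed-dose rule would precipitate withdrawal.** The warning in 2.3.1 is worded for SL-BUP use before XR-NTX is started. Extending it to re-injection is an inference. The documents do not give the duration of blockade and describe naltrexone as eliminated gradually, so a short delay may be harmless.
- **That the discontinuation figures in 2.3.1 give a frequency.** They are 3%, 2%, 1% and 0.3%, or 6.3% in total if they do not overlap. Applied to 45 active-arm participants, 3% to 6.3% would be 1.4 to 2.8 people. But these are rates of stopping XR-NTX treatment, and nothing shows how many would continue SL-BUP. The frequency is unknown.

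The conclusion assumes that no such rule exists in the Manual of Procedures cited in Protocol 14.3, which was not available. The intention-to-treat analysis, alpha and power are unaffected. This is a minor safety point, worth making because the remedy is cheap.

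**What to change.** Replace the sentence in Protocol 6.1.8 with a rule applied identically to active and placebo kits, so that masking holds:

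> Tablets are dispensed only when the scheduled injection has been given. A participant who permanently stops injections also stops tablets and stays in follow-up. Before an injection delayed beyond the visit window in a participant who has continued tablets, record the date of the last tablet and perform COWS; the investigator decides whether a tablet-free interval is needed.

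In Protocol 2.3.1 and 8.7, say that the risk is reduced rather than eliminated.

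In SAP 8.3 and Appendix A(c), add the number of participants by arm with tablets taken beyond the injection interval. Show the number of days as well, because in-window visit timing alone can produce up to 14.

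If the Manual of Procedures already has the rule, a cross-reference in 6.1.8 is enough.

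The cost is one paragraph, two wording edits and one descriptive line. COWS is already a study instrument and injection dates are in source notes (6.1.5). If the dosing log holds only counts, those dates must be entered, and missed-pill counts will make the tablet days approximate. The downside is that a few participants lose tablets after a missed injection, which slightly lowers exposure in the intention-to-treat set.
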